2.3 Randomization

Random treatment-arm allocation will occur at a 1:1 ratio, stratified by study site and by HIV status. Permuted-block randomization will be used to assure balanced groups within each study site and HIV-status subgroup with 30 blocks per site/HIV-status stratum. A list of size 240 [$10 \times (6+8+10)$] would allow each site more than enough randomization slots in case a site is called upon to enroll greater than the projected sample size (approx. $n=80$ HIV negative participants and approx. $n=10$ HIV positive participants per site), or in case of dropouts or randomization errors.

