3. GENERAL DATA ANALYSIS CONSIDERATIONS

3.1 Analysis Set(s)

- **Intent to Treat (ITT):**
All participants enrolled, excluding those who were inappropriately enrolled.
- **Safety:**
There is no formal safety analysis in this study, however, serious adverse events (SAE) will be monitored for all randomized participants.

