8. EFFICACY/EFFECTIVENESS ANALYSES

Primary Outcomes:

Among the enrolled HIV-negative cohort:

- Documented current use of MOUD defined as: alive, retained, with biological evidence of MOUD (defined in section 5) and a current MOUD prescription or proof of current receipt of MOUD from a clinic that does not provide individual MOUD prescriptions (e.g., methadone clinics) at the week 26 visit
- Current use of PrEP defined as: alive, retained, HIV-negative, with detectable PrEP (defined in section 5) at the week 26 visit

For the primary outcome of MOUD use, a Generalized Linear Model (GLM) for binary outcomes using the identity link will be performed with treatment arm and site as covariates. The proportions of participants who meet the MOUD endpoint criteria (by-arm, and by-site-by-arm) at week 26 will be provided along with the estimate and 95% confidence interval for the difference in proportions.

For the primary outcome of PrEP use, a Generalized Linear Model (GLM) for binary outcomes using the identity link will be performed with treatment arm and site as covariates. The proportions of participants who meet the PrEP endpoint criteria (by-arm, and by-site-by-arm) at week 26 will be provided along with the estimate and 95% confidence interval for the difference in proportions.

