10. SECONDARY ENDPOINTS

1. **To evaluate whether “one stop” integrated health services delivered in a mobile unit, supported by peer navigation, compared to peer navigation to similar health services available at community-based agencies, the following endpoint(s) will be assessed:**
 - a) Improves use of MOUD at 52 weeks compared to the active control condition

Outcomes:

- Documented current use of MOUD: alive, retained, with biological evidence of MOUD (as defined above) at the week 52 visit and a MOUD prescription current at 52 weeks after enrollment or proof of current receipt of MOUD from a clinic that does not provide individual MOUD prescriptions (e.g., methadone clinics) at the week 52 visit
- Documented use of MOUD during the study: a MOUD prescription documented during the 52 weeks of study follow-up or proof of current receipt of MOUD from a clinic that does not provide individual MOUD prescriptions (e.g., methadone clinics) during the 52 weeks of study follow-up

These outcomes will be modeled and summarized using the same strategy as specified for the primary outcome in section 8 above.

- b) Increases rates of viral suppression among people enrolled living with HIV, at 26 and 52 weeks

Outcome:

- Among participants living with HIV at enrollment: alive, retained, and virally suppressed (VL <200 copies/mL) at the week 26 and 52 visits, separately.

The proportion of participants achieving the viral suppression outcome will be computed and presented by arm and within site by arm, along with exact Clopper-Pearson 95% confidence intervals using F-quantiles based on the Binomial distribution. No statistical comparisons between treatment arms will be made.

- c) The intervention increases use of PrEP among people without HIV at 26 and 52 weeks

Outcome:

- Among participants without HIV at enrollment: alive, retained, HIV negative, with detectable PrEP drugs in DBS at the week 52 visit
- Among participants without HIV at enrollment: alive, retained, HIV negative, with protective levels of PrEP drugs in DBS samples at the week 26 and 52 visits

A protective level of oral PrEP³ is defined as:

TFV-DP concentrations ≥ 800 fmol/punch in DBS among those tested for Truvada (TDF-FTC)

TFV-DP concentrations ≥ 950 fmol/punch in DBS among those tested for Descovy (TAF-FTC)

A protective level of long-acting PrEP (Cabotegravir) is defined as plasma concentrations above the four times the PA-IC₉₀ of 166 ng/mL – that is, above 664 ng/mL.

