Note: Participants can be non-prevalent (positive tests with tier $< 1:8$) but also not negative for syphilis. Thus, they had syphilis previously, but it is not a prevalent infection.

New syphilis is defined as a positive non-treponemal test and positive treponemal test (regardless of titer value) at a follow-up visit when they were negative at the previous visit.

These outcomes will be modeled and summarized using the same strategy as specified for the primary outcome in section 8 above.

f) Decreases fatal and non-fatal overdose events by 26 and 52 weeks

Outcomes:

- Death, with overdose as cause, collected on or before 26- and on or before 52-week visits, separately.
- Self-report of non-fatal overdose, collected on or before week 26- and on or before 52-week visits, separately.

These outcomes are reported on the SAE log form.

Death, caused by overdose, will be modeled with a time-to-event cox proportional hazards model with treatment arm as a covariate.

Person-time for fatal overdoses will be calculated as follows:

- For those retained (alive) at the visit: time between enrollment and the week 26 or week 52 visit date.
- For those reported deceased by the visit date: time between enrollment and recorded date of death.
- If deceased and no recorded date of death: time between enrollment and the midpoint of last attended visit and termination date.
- Those with no reported death and not retained at week 26 and/or week 52 (or terminated before the visit): use time between enrollment and the last attended visit (or termination date). If no other visit besides enrollment is documented: exclude from the analysis.

Note: Last attended visit can include the enrollment or week 26 visits, an interim visit, or a navigation session

Self-reported non-fatal overdoses will use a Poisson regression model (GLM with log link) with treatment arm as a covariate. We will use the number of reported non-fatal overdoses in the 30 days prior to the respective visit to compare treatment arms.

- g) Increases the proportion of participants with undetectable HCV RNA at 26 and 52 weeks among those with chronic HCV infection at enrollment

Outcome:

- Undetectable HCV RNA at the week 26 and 52 visits (visits analyzed separately) among participants with chronic HCV at enrollment.

The HCV treatment outcome will be modeled and summarized using the same strategy as specified for the primary outcome in section 8 above.

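### Between-arm secondary models that pool both HIV groups leave out HIV status, a randomization stratum, and the two overdose models leave out site as well

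*SAP*

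**What the plan says.** Section 2.3 sets the design: "Random treatment-arm allocation will occur at a 1:1 ratio, stratified by study site and by HIV status". Section 8 introduces both primary outcomes with "Among the enrolled HIV-negative cohort" and analyses each with a "Generalized Linear Model (GLM) for binary outcomes using the identity link will be performed with treatment arm and site as covariates".

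Section 10 carries this model over to several secondary outcomes. Under 1a (MOUD at week 52 and MOUD during the study) it says "These outcomes will be modeled and summarized using the same strategy as specified for the primary outcome in section 8 above". The same sentence closes 1c, 1d and 1e, and 1g has an equivalent one. HCV incidence (1h) has its own Poisson model with arm, site and a person-time offset. For 1f, the fatal-overdose Cox model has arm alone, and so does the non-fatal model: "Self-reported non-fatal overdoses will use a Poisson regression model (GLM with log link) with treatment arm as a covariate".

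The only general efficacy set is the ITT set in section 3.1: "All participants enrolled, excluding those who were inappropriately enrolled". Elsewhere in the SAP, HIV status serves to define populations and to break down tables and listings (baseline data, SAEs, pregnancy). It is a covariate in no model.

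**The concern.** An analysis should normally carry the factors that the allocation was stratified on, or say why it does not. Balancing the arms within strata removes between-stratum variation from the true sampling error of the arm difference. A model without the stratum still counts that variation as noise. Its standard error is then too large, its confidence interval too wide and its test conservative.

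Section 8 escapes this because it analyses one HIV stratum. Its covariate list was built for that cohort and does not suit outcomes that include both HIV groups. Site is also handled unevenly: 1h adjusts for it and 1f does not, with no reason given. What is at stake is some precision on the secondary comparisons and consistency with the design, not their validity.

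**Working it through.** **1. Models set against the strata (site, HIV status)**

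| Outcome | HIV groups included | Covariates besides arm | Stratum left out |
|---|---|---|---|
| Primary MOUD, PrEP (section 8) | HIV-negative only | site | none that matters |
| 1b viral suppression | living with HIV | not modelled | – |
| 1c PrEP | without HIV | site | none that matters |
| 1a MOUD | not stated | site | HIV status, if all ITT |
| 1d substances, 1e STIs, 1g HCV RNA | not limited by HIV status | site | HIV status |
| 1h HCV incidence | not limited by HIV status | site | HIV status |
| 1f fatal overdose (Cox) | not limited by HIV status | none | site and HIV status |
| 1f non-fatal overdose (Poisson) | not limited by HIV status | none | site and HIV status |

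**2. The plan's own figure**

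Inputs from section 2.5: MOUD 25% vs 40%, two-sided 5%, 90% power. Unpooled formula per arm:

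n = (0.25×0.75 + 0.40×0.60) × (1.960 + 1.282)² / 0.15² = 0.4275 × 10.51 / 0.0225 ≈ 200, so 400 in total.

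This reproduces the stated 400; the pooled-variance formula gives 203 per arm, 406 in total. The rates can therefore serve as inputs below.

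**3. Cost of omitting HIV status in 1a**

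Inputs: 450 participants, 225 per arm; 50 living with HIV (sections 2.3 and 2.5), so w = 50/450 = 0.111. Assumptions: HIV-negative rates of 25% and 40%, borrowed from week 26; a 15-point effect in both HIV groups; equal arms within each HIV group; an HIV-positive control rate q that the SAP does not give, so a range is shown.

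- Stratified variance: Vs = {(1−w)(0.25×0.75 + 0.40×0.60) + w[q(1−q) + (q+0.15)(0.85−q)]} / 225
- Unstratified variance: Vu = [m0(1−m0) + m1(1−m1)] / 225, with m0 = (1−w)×0.25 + w×q and m1 = (1−w)×0.40 + w×(q+0.15)
- SE inflation = √(Vu/Vs); actual alpha = 2[1 − Φ(1.96 × inflation)]

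Worked at q = 75%: m0 = 0.3056 and m1 = 0.4556. Vu = 0.4602/225, so SE 0.04523. Vs = 0.4108/225, so SE 0.04273. The ratio is 1.058.

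| q | SE unstratified | SE stratified | Inflation | Actual alpha |
|---|---|---|---|---|
| 10% | 0.04296 | 0.04273 | 0.5% | 0.049 |
| 25% | 0.04359 | 0.04359 | 0% | 0.050 |
| 40% | 0.04415 | 0.04393 | 0.5% | 0.049 |
| 50% | 0.04449 | 0.04387 | 1.4% | 0.047 |
| 60% | 0.04481 | 0.04359 | 2.8% | 0.044 |
| 75% | 0.04523 | 0.04273 | 5.8% | 0.038 |

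With 1:1 allocation in each stratum, the crude and stratified differences estimate the same quantity, so there is no bias.

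**4. Models that cannot be sized**

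For 1d, 1e, 1g and 1h the SAP gives no rates by HIV status. For 1f it gives no overdose rates by site. No gain can be computed for these, and the case rests on consistency with the design.

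**5. What turns on the 1a population**

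On the same borrowed rates, the 95% half-width is 1.96√(0.4275/200) = 9.1 points with 400 participants and 1.96√(0.4275/225) = 8.5 points with 450. If the effect is 15 points in the HIV-negative group and 0, 15 or 30 points in the other 50 (assumed), the pooled estimate is (400×15 + 50×d)/450 = 13.3, 15.0 or 16.7 points.

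**The case against.** The strongest reply is that the omission hardly matters. The SAP expects very different results by HIV status only for HIV-related success (section 2.5), and those outcomes are already analysed within one HIV group. It predicts no such gap for MOUD, substance use, STIs or HCV RNA. Without a wide gap the inflation is at most about half a percent, and the error is on the conservative side. This stands, and it limits the point to a small improvement.

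The second reply is that the remedy has a cost. Sites expect about 10 HIV-positive participants each, so about 5 per arm. An extra term in an identity-link binomial model can push fitted probabilities outside 0 to 1 or stop convergence. Stratifying a Cox model over five sites can lose information if deaths are few. This also stands, and it is why a fallback is needed.

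A reader might infer that the secondary outcomes in general have no fixed population. The text does not support that. Section 3.1 supplies ITT as the default, and 1b, 1c, 1d, 1e, 1g and 1h state their own restrictions. Outcome 1c is telling: it uses the same cross-reference to section 8 yet still specifies "Among participants without HIV at enrollment: alive, retained, HIV negative, with detectable PrEP drugs in DBS at the week 52 visit", which would be redundant if the cross-reference imported the HIV-negative cohort. The likelier reading is that it borrows the model and summaries, not the cohort. Only 1a keeps a real doubt, because it repeats a section 8 outcome and names no population.

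A reader might also infer that a week 52 against week 26 durability comparison would mix populations. No model in the SAP contrasts the arm effects at the two visits, so at most this is a caution when results are read side by side. Nor is a loss of power shown: the SAP states no power for week 52 MOUD.

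**Conclusion.** The point holds as a modest departure from the design. HIV status enters no between-arm model that pools both HIV groups, and the two overdose models also omit site. The arm comparison is not biased and no result would be wrong. For 1a analysed in all ITT participants, the standard error is too large by 0 to 0.5% for HIV-positive control rates of 10 to 40%, rising to about 6% at 75%; actual alpha is then between 0.050 and 0.038. These figures rest on week 26 rates used for week 52, an assumed range for the HIV-positive rate, an equal effect in both groups and 50 HIV-positive participants. The effect on the other models cannot be sized from the SAP. The unstated population in 1a is a missing detail that one sentence would settle.

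**What to change.** - **1a, 1d, 1e, 1g, 1h:** add HIV status to arm and site wherever both HIV groups are pooled. Section 8 and 1c need no change.
- **1f, non-fatal overdose:** add site and HIV status to the Poisson model.
- **1f, fatal overdose:** stratify the Cox model by site if event numbers allow. Set that threshold in advance, and give the reason for leaving HIV status out (few HIV-positive participants, probably few deaths).
- **Fallback:** name one method for use if the identity-link model does not converge or strata are sparse, for example a Mantel–Haenszel risk difference over site and HIV status.
- **1a population:** state whether it is the HIV-negative cohort or all ITT participants.

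The cost is SAP wording only, since both factors are recorded at randomization. The one small downside, convergence or sparse strata, is covered by the fallback.

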 - c) Develop evidence-based guidance for policymakers on the uptake and implementation of integrated health services using peer navigation and mobile health units in urban US regions to address HIV prevention in PWID
 - d) Identify factors that enhance or impede the delivery of integrated health services using a mobile unit, supported by peer navigation, on primary and secondary outcomes, including responding to the impact of COVID-19 on service delivery
- 7) To use mathematical modeling methods to:
 - a) Estimate the effect of integrated health services delivered in a mobile unit, supported by peer navigation, on reducing HIV incidence in PWID and their sexual and injection partners
 - b) Estimate the cost-effectiveness of the integrated health services provided in a mobile unit and supported by peer navigation

Process:

For participants in the intervention arm, assess:

1. Time to provide MOUD treatment, ART (among those who are living with HIV and not on ART at Enrollment) and PrEP (among those who are without HIV at Enrollment)
2. The proportion of participants linked to community based MOUD, ART and PrEP services at 26 weeks

Exploratory Objectives:

Stored samples may be used to analyze HIV subtypes/strains, HIV drug resistance, and the duration of HIV infection. Phylogenetic methods may be used to evaluate behavioral, demographic, and clinical factors associated with viral clusters and transmission dynamics. Stored samples may also be used to characterize HCV strains and the relationship between HIV and HCV infections, and to explore issues related to COVID-19.

Endpoints:***Primary:***

Consistent with the primary study objective to evaluate whether the intervention improves use of MOUD and increases use of PrEP, as measured at 26 weeks among people without HIV, the following endpoints will be assessed:

1. Documented current use of MOUD. At the Week 26 visit:
 - a) Alive
 - b) Retained
 - c) Biological evidence of MOUD (any detectable Methadone or Buprenorphine)
 - d) A MOUD prescription current at the week 26 visit or proof of current receipt of MOUD from a clinic that does not provide individual MOUD prescriptions (e.g., methadone clinics)
2. Among participants who were without HIV at enrollment: alive, retained, without HIV, with detectable PrEP drugs (Truvada or Descovy in dried blood spot (DBS) samples, or Cabotegravir in plasma samples at the week 26 visit

Secondary:

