5. GENERAL ANALYSIS METHODS

Participants characteristics at baseline will include the number of subjects with non-missing value (n), plus frequency and percentage for the categorical variables; and mean, median, standard deviation (SD), minimum (min), and maximum (max) for the continuous variables. Baseline is defined as Enrollment visit, except for data collected at screening and not at enrollment visit. For example, opioids data collected at screening visit will be considered as baseline data.

Any deviations from this statistical plan will be described in the final report. Primary and secondary outcomes will be limited to data collected within the allowable visit window for the week 26 and week 52 visits, respectively.

For all outcomes below, “retained” at 26 weeks is defined as having completed the 26-week visit within the allowable window of 126-308 days from enrollment, and “retained” at 52 weeks is defined as having completed the 52-week visit within the allowable window of 309-449 days from enrollment.

[figure not shown]
For MOUD outcomes, biological detection of Buprenorphine (or Norbuprenorphine or Buprenorphine Glucuronide) or Methadone (or EDDP) will be performed via laboratory analysis of plasma and urine samples. Detectable MOUD is defined as a value above the lower limit of quantitation (LLOQ) for any of the medications or metabolites mentioned above, in either plasma or urine.

For PrEP outcomes, the PrEP regimen tested (Truvada or Descovy in DBS, or CAB-LA in plasma) is determined based upon reported PrEP use. If there is no reported PrEP usage, the default regimen is Truvada. Detectable PrEP is defined as a value above the lower limit of quantitation (LLOQ) for the PrEP regimen tested.

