- h) Decreases HCV incidence at 52 weeks, for those who are HCV negative at enrollment

Outcome:

- HCV antibody positive at the week 52 visit among participants who are HCV antibody negative at enrollment.

HCV incidence will be modeled using Poisson regression (GLM with log link), with treatment arm and site as covariates and person years as an offset. Person time will be computed as the number of years from enrollment to the visit date where infection is first detected for participants with incident HCV infection, and from enrollment to the week 52 visit date (or last available visit) for HCV-negative participants with no incident infection.

2. To evaluate whether 26 weeks of “one stop” integrated health services delivered in a mobile health delivery unit, supported by peer navigation, increases MOUD use, viral suppression, and PrEP use at 26 and 52 weeks compared to enrollment, the following endpoint(s) will be assessed:

- In the intervention arm, change over time in the use of MOUD during the study, comparing documented use of MOUD (biological evidence of MOUD - any detectable medications - and a current MOUD prescription or proof of current receipt of MOUD from a clinic that does not provide individual MOUD prescriptions (e.g., methadone clinics)) at 26 and 52 weeks to documented use of MOUD at enrollment. MOUD use is assumed to be zero at enrollment due to study exclusion criteria. Follow-up endpoints will be defined as alive, retained, and having documented MOUD use.
- Among participants living with HIV at enrollment: change over time in the proportion of people with viral suppression (VL<200 copies/mL), comparing 26 and 52 weeks to enrollment. Follow-up endpoints will be defined as alive, retained, and virally suppressed.

- Among participants who were without HIV at enrollment: change over time in the proportion of people with detectable PrEP drugs in DBS at 26 and 52 weeks compared to enrollment. Follow-up endpoints will be defined as alive, retained, and having detectable PrEP.

The viral suppression outcome will not be modelled. We will report the proportions at enrollment, 26 week and 52-week visits, along with exact Clopper-Pearson 95% confidence intervals using F-quantiles based on the Binomial distribution.

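### Secondary PrEP outcomes are worded as dried-blood-spot only, which contradicts the primary endpoint, Section 5 and the SAP's own plasma threshold, and leaves the classification of cabotegravir users open

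*SAP*

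**What the plan says.** **Primary outcome.** SAP Section 2.2 defines the week-26 PrEP endpoint "with detectable PrEP drugs (Truvada or Descovy in dried blood spot (DBS) samples, or Cabotegravir in plasma samples at the week 26 visit". Section 8 restates it by cross-reference: "alive, retained, HIV-negative, with detectable PrEP (defined in section 5) at the week 26 visit".

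**General rule.** Section 5, introduced as applying to PrEP outcomes, says "the PrEP regimen tested (Truvada or Descovy in DBS, or CAB-LA in plasma) is determined based upon reported PrEP use". It adds: "Detectable PrEP is defined as a value above the lower limit of quantitation (LLOQ) for the PrEP regimen tested". If no PrEP use is reported, Truvada is the default regimen tested.

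**Secondary outcomes** (Section 2.2, repeated in Section 10):
- Objective 1c, detection: "alive, retained, HIV negative, with detectable PrEP drugs in DBS at the week 52 visit".
- Objective 1c, protective level at weeks 26 and 52: the bullet asks for protective levels in DBS samples. Below it, the same item of Section 10 states: "A protective level of long-acting PrEP (Cabotegravir) is defined as plasma concentrations" above 664 ng/mL.
- Objectives 2 and 3, intervention and control arm in turn: "change over time in the proportion of people with detectable PrEP drugs in DBS at 26 and 52 weeks compared to enrollment". Each of these bullets ends with a sentence that defines follow-up success as detectable PrEP and names no sample type.

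None of the secondary PrEP bullets refers to Section 5.

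**The concern.** The SAP provides for cabotegravir measurement only in plasma. An outcome that asks for drug in DBS therefore cannot be met, as written, by someone whose only PrEP is cabotegravir. The restriction appears in both the endpoint list and the analysis section, so it is not a single slip.

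Two things are at stake. First, the week-26 proportion with detectable PrEP could differ between the primary table and the within-arm change table for the same arm and visit. Second, Section 2.1 describes week 52 as the evaluation of durability. If week 26 counts plasma and week 52 does not, a participant who stays on cabotegravir throughout looks like one who stopped.

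The missing-data rule in Section 3.2 does not resolve this. It codes a missed visit as negative, but says nothing about a retained participant who was assigned to plasma testing and has no DBS result. Different programmers could code that person negative, missing or, through Section 5, positive.

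**Working it through.** **1. The one stated figure.** Section 10 sets the cabotegravir threshold at four times 166 ng/mL. 4 × 166 = 664 ng/mL, as stated.

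**2. One participant, two readings.** Take a participant without HIV, retained at both visits, on cabotegravir alone, with plasma above the LLOQ and above 664 ng/mL.

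| Outcome | Secondary bullet read literally | Section 5 and plasma threshold applied |
|---|---|---|
| Week 26 primary (2.2, 8) | success (plasma is named in the primary itself) | success |
| Week 26 change from enrollment (objectives 2, 3) | no qualifying DBS result | success |
| Week 26 protective level (1c) | no qualifying DBS result | success |
| Week 52 detection (1c) | no qualifying DBS result | success |
| Week 52 protective level (1c) | no qualifying DBS result | success |
| Week 52 change from enrollment (objectives 2, 3) | no qualifying DBS result | success |

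The columns agree only on the primary outcome. For the protective level, the literal column also contradicts the plasma criterion printed under the same item, which would have no use if plasma results did not count.

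**3. Possible size (illustration only).** Inputs from Section 2.5: PrEP uptake of 5% (control) and 20% (intervention), and 400 people without HIV, which is 200 per arm at 1:1. These are week-26 planning rates; the SAP gives none for week 52. The share *s* of PrEP users on cabotegravir is **assumed**, since the SAP gives no figure.

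Difference in percentage points if only DBS counts:
- equal share in both arms: (20 − 5) × (1 − s)
- intervention arm only: 20 × (1 − s) − 5
- control arm only: 20 − 5 × (1 − s)

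| s | Equal share | Intervention only | Control only |
|---|---|---|---|
| 0% | 15.0 | 15.0 | 15.0 |
| 10% | 13.5 | 13.0 | 15.5 |
| 20% | 12.0 | 11.0 | 16.0 |
| 30% | 10.5 | 9.0 | 16.5 |
| 50% | 7.5 | 5.0 | 17.5 |

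Power for a two-sided 5% comparison of two proportions (normal approximation, pooled variance under the null, n = 200 per arm) is Φ{[d√n − 1.96√(2p̄(1 − p̄))] / √[p₁(1 − p₁) + p₂(1 − p₂)]}.

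Example, equal share of 20%: p₁ = 0.04, p₂ = 0.16, d = 0.12, p̄ = 0.10. The numerator is 1.697 − 0.832 = 0.866, the denominator 0.416, and the power Φ(2.08) = 98.1%.

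With no cabotegravir use, power is 99.6%. For shares of 10%, 20%, 30% and 50% it is 99.1%, 98.1%, 96.3% and 87.5% if the share is equal, and 98.5%, 95.1%, 86.9% and 47.5% if cabotegravir is used only in the intervention arm.

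**The case against.** The best reply is that Section 5 already settles the matter. Its rule is written for PrEP outcomes in general, sends reported cabotegravir users to plasma, and defines detectability by the regimen tested. The closing sentence of the change-over-time bullets names no sample type, so it is compatible with Section 5. The plasma threshold in Section 10 shows that cabotegravir was meant to count towards the protective level. The change history records that version 2.0 updated PrEP regimen testing and the protective levels, including CAB-LA, which suggests that the DBS phrases were simply left over.

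Much of this stands. A reader might infer that cabotegravir users *are* failures in the secondary analyses, or that the protective-level outcome excludes them. The SAP does not support either: Section 5 offers a competing definition, and the protective-level item contradicts itself rather than excluding plasma. Nor does the text support assuming higher cabotegravir use in the intervention arm.

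What the reply does not do is remove the conflict. A specific outcome definition would ordinarily be taken to prevail over a general rule, and these bullets state a narrower sample type without a cross-reference. The SAP uses such references elsewhere: the primary PrEP outcome points to Section 5, and the week-52 MOUD outcome points back to its earlier definition. Someone programming from the PrEP bullets alone would not count plasma.

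**Conclusion.** The secondary PrEP wording contradicts the primary endpoint, Section 5 and the SAP's own plasma threshold. The classification of participants on cabotegravir alone is therefore ambiguous, and on the literal wording they do not meet the week-52 detection or change-over-time outcomes. This affects secondary outcomes only; the primary PrEP endpoint is clearly defined on this point.

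The size cannot be established from the SAP. With true use of 20% vs 5% and an equal assumed share of 10% to 50% of users on cabotegravir, the literal reading shrinks a 15-point difference to between 13.5 and 7.5 points. With unequal shares, the between-arm error can go either way, as the control-only column shows. The proportion with detectable PrEP within an arm can only be understated. A material loss of power should not be inferred: with an equal share of 20%, power is still 98.1%, and the steep losses need large shares confined to the intervention arm.

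**What to change.** In Sections 2.2 and 10:

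- **Week-52 detection (1c) and change over time (objectives 2 and 3):** replace the DBS phrase with *detectable PrEP (defined in section 5)*, as Section 8 does for the primary outcome. In the change analyses this should hold at enrollment as well as at weeks 26 and 52, so that both ends of the comparison use one definition.
- **Protective level (1c):** word it as *protective levels of PrEP drugs in DBS (Truvada or Descovy) or plasma (cabotegravir)*, and apply the thresholds already stated at both visits.

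For detection, the cross-reference is safer than naming an analyte. TFV-DP appears in the SAP only in the protective-level thresholds, so writing it into the detection outcomes would create a new mismatch with the primary endpoint.

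Within the SAP this costs wording only, because the plasma assay rule and the threshold are already there. Only the SAP was reviewed, so the protocol's endpoint wording should be checked for the same phrase.
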